Measure	Variable	Analysis and Imputation Method	Datapoint Sets	TPI*	Analysis Type
SRI-4	Proportion of patients achieving SRI-4 response	Logistic Regression, NRI + MI	PPCV	Week 24 visit, Week 52 visit	Primary endpoint (Week 52); major secondary (Week 24)
		Logistic Regression, NRI	PP	Week 24 visit, Week 52 visit	Supplemental
		Logistic Regression, NRI	AC	Week 24 visit, Week 52 visit	Supplemental
		Logistic Regression, NRI + MI	PPCV, Per Protocol population	Week 52 visit	Supplemental
		Logistic Regression, NRI + MI	PPCV	Week 52 visit	Sensitivity (Tipping point analysis)
SRI-x (where x is 5, 6, 7, 8)	Proportion of patients achieving SRI-x response ^a	Logistic Regression, NRI	PP	Week 52 visit	Secondary endpoint
SLEDAI-2K	Change from baseline in total SLEDAI-2K through Week 52 visit	MMRM	PP	Week 52 visit	Secondary endpoint
	Proportion of patients achieving reduction of ≥ 4 points from baseline	Logistic Regression, NRI + MI	PPCV	Week 52 visit	Secondary endpoint
		Logistic Regression, NRI	PP	Week 52 visit	Secondary endpoint
	Proportion of patients with no worsening in SLEDAI-2K compared with baseline	Logistic Regression, NRI + MI	PPCV	Week 52 visit	Supplemental
		Logistic Regression, NRI	PP	Week 52 visit	Supplemental
	Proportion of patients with improvement in each SLEDAI-2K individual organ systems versus baseline ^b	Logistic Regression, NRI	PP	Week 52 visit	Secondary endpoint
	Proportion of patients with worsening in each SLEDAI-2K individual organ systems versus baseline ^c	Logistic Regression, NRI	PP	Week 52 visit	Secondary endpoint

Description of Efficacy/Health Outcomes Analyses

Measure	Variable	Analysis and Imputation Method	Datapoint Sets	TPI*	Analysis Type
BILAG	Proportion of patients with no new BILAG A and no more than 1 new BILAG B disease activity score (compared with baseline)	Logistic Regression, NRI + MI	PPCV	Week 52 visit	Secondary endpoint
		Logistic Regression, NRI	PP	Week 52 visit	Secondary endpoint
	Proportion of patients with reduction of all baseline BILAG A to B/C/D and baseline BILAG B to C/D and no BILAG worsening in other organ systems, where worsening is defined as ≥ 1 new BILAG A or ≥ 2 new BILAG B	Logistic Regression, NRI+MI	PPCV	Week 52 visit	Supplemental
		Logistic Regression, NRI	PP	Week 52 visit	Supplemental
	Proportion of patients with improvement in each BILAG individual organ systems versus baseline ^d	Logistic Regression, NRI	PP	Week 52 visit	Exploratory endpoint
	Proportion of patients with worsening in each BILAG individual organ systems versus baseline ^e	Logistic Regression, NRI	PP	Week 52 visit	Exploratory endpoint
PGA	Proportion of patients with no worsening in PGA (compared with baseline)	Logistic Regression, NRI+MI	PPCV	Week 52 visit	Secondary endpoint
		Logistic Regression, NRI	PP	Week 52 visit	Secondary endpoint
	Change from baseline in PGA score over time through Week 52 visit	MMRM	PP	Week 52 visit	Secondary endpoint
BICLA	Proportion of patients achieving BICLA response	Logistic Regression, NRI + MI	PPCV	Week 52 visit	Secondary endpoint
		Logistic Regression, NRI	PP	Week 52 visit	Secondary endpoint
		Logistic Regression, NRI	AC	Week 52 visit	Secondary endpoint

Description of Efficacy/Health Outcomes Analyses

Measure	Variable	Analysis and Imputation Method	Datapoint Sets	TPI*	Analysis Type
28 Tender/ Swollen Joint Count	Change from baseline in tender joint count	MMRM	PP	Week 52 visit	Secondary endpoint
	Change from baseline in swollen joint count	MMRM	PP	Week 52 visit	Secondary endpoint
CLASI Activity Score	The proportion of patients with \geq 50% reduction from baseline in total activity score ^f	Logistic Regression, NRI	PP	Week 52 visit	Secondary endpoint
SFI	Annualized severe flare rate	Negative binomial regression	PPCV	Through Week 52 visit	Secondary endpoint
		Negative binomial regression	PP		Supplemental
		Negative binomial regression	AC		Supplemental
	Annualized mild/moderate flare rate	Negative binomial regression	PP	Through Week 52 visit	Secondary endpoint
	Annualized flare rate (any severity)	Negative binomial regression	PP	Through Week 52 visit	Secondary endpoint
	Time to first severe flare	Cox regression	PPCV	Through Week 52 visit	Major secondary (Principal inference)
			PP		Supplemental
			AC		Supplemental
	Time to first flare (any severity)	Cox regression	PP	Through Week 52 visit	Secondary endpoint
LLDAS	Proportion of patients who achieve a LLDAS	Logistic Regression, NRI + MI	PPCV	Week 52 visit	Major secondary (Principal inference)
		Logistic Regression, NRI	PP		Supplemental
		Logistic Regression, NRI	AC		Supplemental

Description of Efficacy/Health Outcomes Analyses

Measure	Variable	Analysis and Imputation Method	Datapoint Sets	TPI*	Analysis Type
Corticosteroid Sparing	Proportion of patients receiving > 7.5 mg/day prednisone at baseline able to reduce prednisone (or equivalent) dose by $\geq 25\%$ to a prednisone equivalent dose of ≤ 7.5 mg/day maintained between Week 40 and Week 52 visit ^g	Logistic Regression, NRI + mLOCF	PPCV	Week 52 visit	Major secondary (Principal inference)
		Logistic Regression, NRI	PP		Supplemental
		Logistic Regression, NRI	AC		Supplemental
	Proportion of patients receiving > 7.5 mg/day prednisone at baseline able to reduce prednisone (or equivalent) dose by $\geq 25\%$ maintained between Week 40 and Week 52 visit ^g	Logistic Regression, NRI + mLOCF	PPCV	Week 52 visit	Supplemental
		Logistic Regression, NRI	PP		Supplemental
	Proportion of patients receiving > 7.5 mg/day prednisone at baseline able to reduce prednisone (or equivalent) dose to ≤ 7.5 mg/day maintained between Week 40 and Week 52 visit ^g	Logistic Regression, NRI + mLOCF	PPCV	Week 52 visit	Supplemental
		Logistic Regression, NRI	PP		Supplemental
	Change from baseline in prednisone dose	MMRM	PP	Week 52 visit	Secondary endpoint
	Proportion of patients able to discontinue corticosteroids and maintained through Week 52 visit ^h	Logistic Regression, NRI	PP	Week 52 visit	Secondary endpoint
Worst Pain NRS	Change from baseline in Worst Pain NRS	MMRM+MI	PPCV	Week 52 visit	Major secondary (Principal inference)
		MMRM	PP		Supplemental
		MMRM	AC		Supplemental

Description of Efficacy/Health Outcomes Analyses

Measure	Variable	Analysis and Imputation Method	Datapoint Sets	TPI*	Analysis Type
FACIT-Fatigue	Change from baseline in FACIT-Fatigue total score	MMRM+MI	PPCV	Week 52 visit	Major Secondary (Principal inference)
		MMRM	PP		Supplemental
		MMRM	AC		Supplemental
Worst Fatigue NRS	Change from baseline in Worst Fatigue NRS	MMRM	PP	Week 52 visit	Secondary endpoint
Worst Joint Pain	Change from baseline in Worst Joint Pain NRS	MMRM	PP	Week 52 visit	Secondary endpoint
Joint Stiffness Duration	Change from baseline in Joint Stiffness Duration	Wilcoxon rank-sum with mLOCF	PP	Week 52 visit	Secondary endpoint
Joint Stiffness Severity	Change from baseline in Joint Stiffness Severity	MMRM	PP	Week 52 visit	Secondary endpoint
Patient Global Impression of Severity	Change from baseline in Patient Global Impression of Severity	MMRM	PP	Week 52 visit	Secondary endpoint
Patient Global Impression of Change	Change from baseline in Patient Global Impression of Change	ANOVA with mLOCF	PP	Week 52 visit	Secondary endpoint
SLICC/ACR	Change from baseline in SLICC/ACR	ANCOVA with mLOCF	PP	Week 52 visit	Exploratory endpoint
SF-36 V2 acute	Change from baseline in MCS	MMRM	PP	Week 52 visit	Secondary endpoint
	Change from baseline in physical component score (PCS)	MMRM	PP	Week 52 visit	Secondary endpoint
	Change from baseline in domain scores SF-36 health survey version 2 acute	MMRM	PP	Week 52 visit	Secondary endpoint
EQ-5D-5L	Change from baseline in EQ-5D-5L US/UK population-based index scores and VAS	MMRM	PP	Week 52 visit	Secondary endpoint
	Proportion of patients with no problem in each EQ-5D-5L item score	Logistic Regression, NRI	PP	Week 52 visit	Secondary endpoint

Description of Efficacy/Health Outcomes Analyses

Measure	Variable	Analysis and Imputation Method	Datapoint Sets	TPI*	Analysis Type
WPAI-Lupus	Change from baseline in WPAI-Lupus ⁱ	MMRM	PP	Week 52 visit	Secondary endpoint

Abbreviations: AC = as collected; ACR = American College of Rheumatology Damage Index; ANCOVA = analysis of covariance; ANOVA = analysis of variance; BICLA = British Isles Lupus Assessment Group Based Composite Lupus Assessment; BILAG = British Isles Lupus Activity Group; CLASI = Cutaneous Lupus Erythematosus Disease Area and Severity Index; EQ-5D-5L = European Quality of Life-5 Dimensions-5 Level; FACIT = Functional Assessment of Chronic Illness Therapy; LLDAS = Lupus Low Disease Activity State; MCS = mental component score; MI = multiple imputation; mITT = modified intent-to-treat; mLOCF = modified last observation carried forward; MMRM = mixed model for repeated measures; NRI = non-responder imputation; NRS = Numeric Rating Scale; PCS = Physical Component Summary; PGA = Physician's Global Assessment; PP = per protocol; PPCV = per protocol COVID free; SFI = SLEDAI Flare Index; SLE = Systemic Lupus Erythematosus; SLEDAI-2K = Systemic Lupus Erythematosus Disease Activity Index 2000; SF-36 = Short Form 36; SRI-4 = SLE Responder Index; SLICC = Systemic Lupus International Collaborating Clinics; TPI = time point of interest; UK = United Kingdom; US = United States; VAS = visual analogue scale; WPAI-Lupus = Work Productivity and Activity Impairment Questionnaire: Lupus V2.0.

- ^a Population is a subset of mITT which includes patients with SLEDAI-2K score $\geq x$ at baseline (where x is 5, 6, 7, 8) for each SRI-x responder analysis.
- ^b Population is a subset of mITT which includes patients with SLEDAI-2K score >0 within the organ domain at baseline.
- ^c Population is a subset of mITT which includes patients with at least one SLEDAI-2K item = 0 in the organ domain at baseline.
- ^d Population is a subset of mITT which includes patients with BILAG A or B in the organ domain at baseline.
- ^e Population is a subset of mITT which includes patients without BILAG A in the organ domain at baseline.
- ^f Population is a subset of mITT which includes patients with CLASI total activity score ≥ 10 at baseline.
- ^g Population is a subset of mITT which includes patients with > 7.5 mg/day prednisone at baseline. The logistic regression model covariates include treatment groups, baseline disease activity (total SLEDAI-2K <10 ; ≥ 10) and region (North America, Central/South America/Mexico, Europe, Asia and Rest of World).
- ^h Population is a subset of mITT which includes patients with > 0 mg/day prednisone at baseline.
- ⁱ For absenteeism score, presenteeism score, and work productivity loss score, population is a subset of mITT which includes patients who had employment status of Yes at baseline.
- * Assessments collected at multiple visits will be analyzed at each visit, in addition to the primary time point listed in the table.

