		BILAG improvement	Reduction of all baseline BILAG A to B/C/D and baseline BILAG B to C/D and no BILAG worsening in other organ systems, where worsening is defined as ≥ 1 new BILAG A or ≥ 2 new BILAG B	Missing if any of 9 domains at baseline or at the visit remains missing after instrument level imputation rules are applied except when the missing is at the baseline (any one or all domains) and the value at the visit is not A or B, then the other non-missing organ domains will be used to determine the response status.

Description and Derivation of Efficacy/Health Outcomes Measures and Endpoints

Measure	Description	Variable	Derivation/Comment	Definition of Missing
		No BILAG worsening	No new BILAG A and no more than 1 new BILAG B disease activity score (both compared with baseline), where worsening is defined as ≥ 1 new BILAG A or ≥ 2 new BILAG B, both compared with the baseline. The baseline BILAG A improved to BILAG B at the visit will not be considered as the new BILAG B.	Missing if any of 9 domains at baseline or at the visit remains missing after instrument level imputation rules are applied except when the baseline (any one or all domains) is BILAG A and the value at the visit is missing, then the other non-missing organ domains will be used to determine the response status.
		Individual Organ Domain Improvement Defined by BILAG	Among patients with BILAG A or B at baseline and able to reduce the baseline BILAG A to B/C/D and BILAG B to C/D for each organ domain, separately.	Missing if baseline or value remains missing after instrument level imputation rules are applied.
		Individual Organ Domain Worsening Defined by BILAG	Among patients without BILAG A at baseline, an increment of baseline BILAG B/C/D/E to A or baseline BILAG C/D/E to B for each organ domain, separately.	Missing if baseline or value remains missing after instrument level imputation rules are applied.

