PGA	The PGA is the physician's assessment of the patient's overall disease activity due to SLE. It is scored using a visual analog scale where 0 mm indicates no disease activity and 100 mm indicates the most severe disease activity possible. There are benchmarks of 0 (0 mm), 1 (33 mm), 2 (67 mm), and 3 (100 mm) on the line corresponding to no, mild, moderate, and severe SLE disease activity, respectively.	PGA score PGA category	Permitted range of values is from 0 to 100 mm. PGA categories are defined as: None (0) = '0 mm', Mild (>0 and <1.5) = ' >0 to < 50 mm', Moderate (≥ 1.5 to ≤ 2.5) = ' ≥ 50 mm to ≤ 83 mm', Severe (>2.5) = ' >83 mm'.	If the visit occurred, data can be carried forward if obtained within 36 days of visit; otherwise missing.
		No worsening in PGA	Worsening is defined as an increase of ≥ 0.3 points (10 mm) from baseline. Therefore, no worsening is defined as any decrease, no change, or <0.3 points (10 mm) increase from baseline.	Missing if baseline or value remains missing after instrument level imputation rules are applied.
		PGA ≤ 1	PGA ≤ 33 mm	Missing if value remains missing at the visit after instrument level imputation rules are applied.

Description and Derivation of Efficacy/Health Outcomes Measures and Endpoints

Measure	Description	Variable	Derivation/Comment	Definition of Missing
BICLA	BICLA is a composite index to measure overall improvement in disease activity (BILAG) while ensuring there is no worsening in other organ systems (SLEDAI and PGA).	BILAG Based Composite Lupus Assessment	
 Reduction of all baseline BILAG A to B/C/D and baseline BILAG B to C/D and no BILAG worsening in other organ systems, where worsening is defined as ≥ 1 new BILAG A or ≥ 2 New BILAG B No worsening from baseline in SLEDAI-2K, where worsening is defined as an increase of >0 points from baseline in SLEDAI-2K No worsening from baseline in participants' lupus disease activity, where worsening is defined by an increase ≥ 0.30 points on a 3-point PGA VAS. 	Missing if any component (BILAG, SLEDAI or PGA) remains missing after each instrument level imputation rule is applied.

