Abbreviations: ACR = American College of Rheumatology Damage Index; BILAG = British Isles Lupus Activity Group; BICLA = British Isles Lupus Assessment Group Based Composite Lupus Assessment; CLASI = Cutaneous Lupus Erythematosus Disease Area and Severity Index; CNS = Central Nervous System; EQ-5D-5L = European Quality of Life–5 Dimensions–5 Level; FACIT = Functional Assessment of Chronic Illness Therapy; LLDAS = Lupus Low Disease Activity State; MCS= Mental Component Score; NRS = Numeric Rating Scale; PCS= Physical Component Summary; PGA = Physician's Global Assessment of Disease Activity; SF-36 = Short Form 36; SFI = SLEDAI Flare Index; SLE = Systemic Lupus Erythematosus; SLICC = Systemic Lupus International Collaborating Clinics; SRI-4 = SLE Responder Index; SLEDAI-2K = Systemic Lupus Erythematosus Disease Activity Index 2000; UK = United Kingdom; US = United States; VAS = visual analogue scale; WPAI:Lupus = Work Productivity and Activity Impairment – Lupus.

Note: Additional supplemental and sensitivity analyses are described in Section 6.10.3.3.

The datapoint sets are defined to estimate the estimands in [Table JAIA.6.5](#). The mITT population will be included in the analysis according to the treatment they were randomized, unless otherwise specified in [Table JAIA.6.6](#).

Patients who are imputed as nonresponders due to a qualifying intercurrent event for binary categorical efficacy variables, will be defined as such from the time of qualifying event, plus 1 day, onward.

Table JAIA.6.5. Datapoint Sets for Use in Efficacy/Health Outcomes Analyses

Datapoint sets	Definition of Missing Data Due to ICEs	Estimand of Interest

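### BICLA and composite BILAG improvement have no baseline BILAG A or B requirement, so read literally a patient with nothing to improve can be scored a responder

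*SAP*

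**What the plan says.** Table JAIA.6.4 (SAP section 6.10.1) defines BILAG improvement, and repeats it as the first BICLA component, as "Reduction of all baseline BILAG A to B/C/D and baseline BILAG B to C/D and no BILAG worsening in other organ systems". The threshold for worsening in this rule is at least one new A or at least two new B scores, so a single new B is tolerated. The other two BICLA components are "No worsening from baseline in SLEDAI-2K, where worsening is defined as an increase of >0 points from baseline in SLEDAI-2K" and the corresponding PGA criterion, "where worsening is defined by an increase ≥ 0.30 points on a 3-point PGA VAS".

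The missing-data rule for BILAG improvement sets the endpoint to missing if any of the nine domains is missing at baseline or at the visit, "except when the missing is at the baseline (any one or all domains) and the value at the visit is not A or B". In that case the remaining non-missing domains decide the response.

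On population, section 6.10.1 states: "The mITT population will be included in the analysis according to the treatment they were randomized, unless otherwise specified in" Table JAIA.6.6. In that table the row "Proportion of patients achieving BICLA response" (PPCV, PP and AC) and the composite BILAG-improvement row (PPCV and PP) carry no subset footnote. The single-domain BILAG improvement row carries footnote d: "Population is a subset of mITT which includes patients with BILAG A or B in the organ domain at baseline".

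**The concern.** The BILAG condition runs over all baseline A and B scores. If there are none, it is satisfied with nothing to reduce, and every other BICLA condition asks only for absence of worsening. Yet Table JAIA.6.4 describes BICLA as an index of overall improvement measured by BILAG.

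The SAP gives no rule for such a patient, and its population rule does not remove them, although it does restrict the single-domain version built from the same letters. Two programmers could code the same patient in opposite ways. If such patients are enrolled and scored as responders, response rates in every arm contain people who had nothing to improve, and the difference between arms is diluted.

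**Working it through.** **1. The rule applied to example profiles.** Nine domains. *Literal* means the reduction condition is met when there is no baseline A or B. *Strict* means at least one A or B must be present to be reduced.

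| Baseline | Visit | Literal | Strict |
|---|---|---|---|
| only C/D/E | unchanged | improved | not improved |
| only C/D/E | one new B | improved | not improved |
| only C/D/E | two new B | not improved | not improved |
| one B | B unchanged | not improved | not improved |
| one B | B to C | improved | improved |

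The readings differ only for patients without a baseline A or B. The SAP does not say which applies. The missing-baseline exception leans towards the literal reading, since it allows a status to be derived for a domain whose baseline letter is unknown, so long as the visit letter is not A or B.

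**2. Wholly missing baseline.** If all nine baseline letters are missing and no visit letter is A or B, the exception applies. It then defers to the other non-missing domains, but no domain has both a baseline and a visit letter, so no reduction can be judged.

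**3. Check of the power formula on the plan's own figure.** SAP section 5.2 gives about 750 patients randomized 1:1:1 (250 per arm), 40% on placebo, a 17-point difference and two-sided α of 0.05. The chi-square formula is

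power = Φ[(d − 1.96·se₀)/se₁], with se₀ = √(2·p̄(1−p̄)/n) and se₁ = √((p₀(1−p₀) + p₁(1−p₁))/n).

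With p₀ = 0.40, p₁ = 0.57 and n = 250 this gives 96.9%, consistent with the stated >90%. That figure is for SRI-4; the SAP states no power for BICLA.

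**4. Dilution.** Let q be the share without baseline A or B and r their response rate, equal in both arms. Each arm's rate is p = (1−q)·p_AB + q·r, so the difference is (1−q) times the difference in patients with A or B, whatever r is.

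Assumptions, none from the SAP: 30% vs 45% in patients with baseline A or B, r = 65%, 250 per arm.

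| q | Rates, all mITT | Difference | Power, all mITT | Power, A/B subset |
|---|---|---|---|---|
| 5% | 31.75% vs 46.00% | 14.25 | 91% | 92% (n = 237.5) |
| 10% | 33.5% vs 47.0% | 13.5 | 87% | 91% (n = 225) |
| 20% | 37.0% vs 49.0% | 12.0 | 78% | 88% (n = 200) |

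Example at 5%: 0.95 × 0.30 + 0.05 × 0.65 = 0.3175, and 0.95 × 0.45 + 0.05 × 0.65 = 0.46. Varying r from 50% to 80% moves power by about 1 point or less.

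**5. Sensitivity to the assumed rates.** Borrowing the SRI-4 rates (40% vs 57%) with r from 60% to 80%, the difference is about 16.2, 15.3 and 13.6 points at q = 5%, 10% and 20%. Power is 95.3%, 93% and 86–87% in all mITT, against 96.2%, 95.3% and 92.8% in the subset.

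**6. Under the strict reading.** Setting r = 0 gives the same (1−q) shrinkage, because these patients stay in the denominator as certain non-responders. The choice of denominator matters under either reading.

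**The case against.** **The affected group may be empty.** Section 4 of the SAP leaves the population of interest to the protocol's entry criteria. If those require BILAG A or B activity, few or no patients are affected. This stands. A reader might infer from the yes/no rows for baseline BILAG involvement in Appendix 2 that such patients exist. They do not show it: the involvement rows are per organ domain, and a patient in neither of the next two rows (at least one A; no A but at least two B) could still have one B.

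**The SAP never says that such a patient counts as improved.** Reduction can be read as needing something to reduce. That also stands: the defect is an unstated scoring rule whose literal reading allows a response.

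**Not worsening is not sufficient by itself.** Under NRI (section 6.4.2.1), missing response data mean non-response, and in PPCV and PP data after prohibited medication or treatment discontinuation are set to missing (Table JAIA.6.5). Any SLEDAI-2K rise also fails BICLA. To say that these patients respond merely by not worsening would be too strong.

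**The footnote contrast is uneven.** Footnotes a and b remove patients who could not respond, which is the opposite problem. The inconsistency rests on footnote d, which concerns the same BILAG letters.

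**A wholly missing baseline is remote.** Section 6.3 takes the last non-missing pre-dose value as baseline. The case should be rare, but the exception names it expressly and does not resolve it.

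**The illustrative rates are assumptions, and equal response in both arms is conservative.** Correct. Under that assumption the effect is dilution and cannot create a benefit.

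**Conclusion.** The point holds as a gap in the definition and an inconsistency in the analysis population. As written, both composites run in all mITT patients with no baseline A or B requirement. On the literal reading, a patient with no baseline A or B, or with a wholly missing baseline BILAG and no A or B at the visit, can be scored a responder.

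Its size depends on a share that the SAP does not give. With equal response in both arms among such patients, the loss is that share of the true difference: 0.75 of 15 points at 5% and 1.5 at 10%. At a share of zero nothing changes.

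The reach is limited. A reader might take BICLA for the trial's main second composite, but Table JAIA.4.1 lists it among the other secondary endpoints without multiplicity control, whereas LLDAS is a composite among the major secondary endpoints. Composite BILAG improvement is supplemental. No primary or major secondary inference is affected. A cheap improvement is worth making.

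**What to change.** In Table JAIA.6.6, add a footnote to the BICLA row and the composite BILAG-improvement row limiting the population to mITT patients with BILAG A or B in at least one organ domain at baseline, in line with footnote d. Keep the all-mITT version as supplemental, and state there how a patient without baseline A or B is scored.

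In the missing rule for BILAG improvement in Table JAIA.6.4, delete the words *or all* from the exception, so that a wholly missing baseline BILAG is treated as missing and falls to non-response under NRI. The remaining wording should make clear that it covers a baseline missing in some but not all domains.

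The cost is SAP wording and one baseline population flag. The downside is a slightly smaller BICLA denominator, for example 225 rather than 250 per arm at an assumed 10% share. Because the flag is defined at baseline, it does not depend on post-randomization data.
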